The study population will include Veterans 18-75 years old. They will be men or women from the greater Providence area receiving care at the VA who have been discharged from active duty, or who served in the National Guard or reserve units.

Two groups will be recruited. One group will consist of Veterans admitted to the PVAMC psychiatric inpatient unit or medical unit or identified in outpatient settings for suicide attempt or suicidal ideation with any degree of suicide plan, and/or intent to attempt suicide. This group of Veterans may be enrolled into either active or sham TMS+BCBT, if eligible. The second group will consist of DSM-V diagnosis-matched Veterans without current suicidality to act as controls. Controls will also be matched for age ± 5 years, and sex. The control Veterans, if eligible, may be enrolled in the neuroimaging and cognitive battery, and not be eligible to receive the TMS+BCBT intervention. The matching procedure is used to limit the influence disorder-specific characteristics, sex, and age-related brain/cognitive differences on group comparisons. If we are unable to meet annual recruitment goals, sex differences will be handled through statistical covariation and strata for age-matching will be broadened (± 10 years).

D2. Participant Selection:

Participants will consist of Veteran inpatients or outpatients of the Providence VAMC with active suicide ideation or related behaviors, and non-suicidal Veteran controls. The inclusion and exclusion criteria are as follows:

D2.1. Inclusion criteria:

Inclusion criteria for all participants:

- 1) Participants must be Veterans aged 18-75 discharged from active duty, National Guard, or reserves units, receiving care at the VA. They must be able to comply with all study related procedures and visits and be

capable of independently reading and understanding study materials and providing informed consent.

Inclusion criteria for Veterans with suicidal thoughts and behaviors:

- 1) Admission to a hospital or identified in outpatient settings within 2 weeks of suicidal ideation with any methods, intent and/or plans, or within 2 weeks after an attempt as

indicated on hospital chart and confirmed by administration of the Columbia Suicidal Severity Rating Scale (C-SSRS).

Inclusion criteria for non-suicidal Veterans (controls)

- 1) No evidence of current suicidality in the medical record or endorsement of current suicidal thoughts and behaviors on the C-SSRS.

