Follow-up assessments will be conducted in-person or if necessary, by telephone 6, 12, and 24 months from the start of the intervention period. When assessments are conducted remotely, de-identified data may be collected by study staff at home due to remote connection issues (due to COVID-19). To reduce attrition, subjects will be paid \$50 in electronic funds transfer (EFT) or gift cards for completion of each follow-up appointment. Veterans participating in TMS+BCBT and neuroimaging will attend follow-up visits at 6, 12, and 24-months. Veterans only participating in TMS+BCBT will attend follow-up visits at 6- and 12-months. Veterans and matched controls participating only in the neuroimaging and cognitive battery will attend follow-ups at 6-, 12-, and 24-months.

D4.5.1 Blinded Assessment Administration: At the intervention endpoint visit, and 6-, 12-, and 24-month follow-up visits, assessments will be administered by study personnel who are blind to TMS condition (active vs. sham). For veterans who participate in the intervention component of the study, these assessments will not be administered by the study therapist or TMS provider even though they are also blind to the TMS condition. All study personnel will be blind to the study condition at baseline.

D5. Electronic Health Record (EHR) Data Extraction

Study staff will manually extract EHR data from participants' VA CPRS files. Extracted values will be entered into VA REDCap in anonymized format (by patients' study ID only). The initial data extraction will occur at baseline no later than one week of the participant's MRI Visit or beginning of intervention. Subsequent data extractions will take place six months, one year, and two years after starting intervention. At each time point (baseline,

+6months, +1 year, +2 years), data for the current month, and for each of the 12 prior months will be extracted.

D5.1 EHR predictor extraction:

Participants' CPRS files will be manually reviewed by the PI or by trained study staff. The following data types will be manually extracted from CPRS files: 1) Health services utilization; 2) pharmaceutical utilization; 3) changes in pharmaceutical utilization; 4) mental health diagnoses. Factors under consideration were selected based on prior demonstrations of machine learning applied to EHR ³⁹⁻⁴¹. Related information such as names of medications and medical conditions will also be extracted.

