D5.2 EHR variable construction: EHR measures are listed in Table 5. Monthly EHR sums will be averaged by quarter and by year. If categorical variables change over an aggregated time point, the most consistent designation over the analyzed epoch will be used.

Health Services Utilization
Outpatient Visits (any service)
Outpatient Visits (MH service)
Emergency or Urgent Care Visits
Inpatient MH
Inpatient (any service)
Pharmaceutical Utilization
Antidepressant
Antipsychotic
Mood Stabilizer
Anxiolytics
Other medications (non-psychiatric)
Change in Pharmaceutical
Antidepressant
Antipsychotic
Mood Stabilizer
Anxiolytics
Other medications (non-psychiatric)
Mental Health (Current and Lifetime)
Depression
Bipolar disorder
Schizophrenia or schizoaffective disorder
Generalized Anxiety Disorder
Posttraumatic Stress Disorder
Specific Phobia
Panic Disorder
Social Phobia
Personality Disorder
ADHD
SUD
Gambling Disorder
Eating Disorders
Suicidality

Table 5. EHR data extracted at baseline and follow-

E. DATA ANALYSIS

E1. Design and Sample Size

This is a single-site, two-arm RCT with individual participant urn randomization. We propose to randomize 130 Veterans. Approximately 65 will be randomized to active TMS+BCBT and 65 participants will be randomized to sham TMS+BCBT. Recruitment for the intervention will cease once randomization goals are met (i.e. n= ~65 Veterans per condition). Additionally, we will be enrolling 60 Veterans, who will be matched on age (within 5 years), primary psychiatric diagnosis, and sex, for a total of 190 Veterans to be enrolled. A subsample of these veterans (120 in total; one group (n=30) with suicide ideation and another group (n=30) with suicide attempts; and controls (n=60) will be used in the analyses of brain-based biomarkers for suicidality. Veterans will be assessed at the study timepoints outlined in C3. Assessments.

E1.1 Overall Analytic Approach across Aims

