Design considerations & alternative strategies for Aim 2. This design uses a categorical factor to define groups that approximates risk by history of attempt versus ideation, based on the strength of previous attempt as a risk factor for subsequent attempts. While straight-forward, we acknowledge that within-group heterogeneity may invalidate this grouping strategy. For instance, the ideation group could contain a significant number of Veterans with highly detailed suicide plans that have begun obtaining means that would be better classified as high-risk. In recognition of this issue, we will also compute empirically-determined risk categorization thresholds based on Beck Lethality Scale, Suicide Intent Scale, and Scale for Suicide Ideation scores. Alternatively, we may use continuous variables operationalizing suicidal planning, intent, or lethality for these analyses.

E3.3 (Exploratory) Integrate EHR data and neurocognitive markers into predictive models of STBs.

We will combine EHR data and objective cognitive measures forming a high-dimensional, multi-modal dataset. Machine learning algorithms will be applied to examine the predictive utility of this approach.

Rationale: Machine learning algorithms can accommodate large predictor sets and can model complex interactions among factors. Models built on EHR outperform traditional models with predictive accuracy in excess of AUC +0.70. We will subject an EHR dataset enriched with additional, objective, cognitive measures of suicidality (defined in Aims 1 & 2) to machine learning classification. Three types of supervised machine learning models (described below) will be used for this exploratory analysis. Models will be constructed both with, and without, Aim 1 & 2 measures to test if their inclusion improves suicide prediction.

Data sources: Aggregated EHR data (Section D6.2) and subject-level performance outcomes on the reward expectancy scanned task, Delay Discounting task, Iowa Gambling Task, Flanker Task, Dimensional Card Sort Task, and SSRT task.

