General approach: The dataset comprised of subject-level aggregated EHR variables and behavioral outcomes from cognitive control and reward tasks will be treated as a “discovery data set,” meaning that it will be used to train machine-learning algorithms and make initial identifications of subsets of the dataset associated with distinct suicide outcomes. Classifier training, cross-validation, and optimization will be performed using this discovery data set. The goal is to predict participants with: 1) history of attempt, 2) suicidal ideation without history of attempt, 3) no history of STBs. Future studies will attempt to replicate findings in an independent sample.

Software: Part of this exploratory aim involves testing implementations against one another. Modeling will be carried out using Julia⁶⁴, an open-source computing language, MATLAB, and R.

Machine learning algorithms:

Elastic Net Regularized Logistic Regression⁶⁵ Unlike other regularized regression methods such as ridge or lasso, elastic net models are stable when multicollinearity amongst

predictors is high. Elastic net regularization penalizes model complexity by specifically modeling overfitting simultaneously combining the shrinkage and recovery approaches of lasso and ridge regularization. This means that coefficients are all retained but undergo shrinkage toward zero. We will use a 10-fold cross-validation to assess the performance of the classifier.

Random forest machine clustering Random forest clustering is a tree-based supervised learning algorithm that can handle high multi-collinearity and is robust to overfitting [95]. Decision trees are built by recursively subsampling predictors from the training dataset [95,96]. At each “split” of a tree, the algorithm searches for a given variable and the binary decision that splits the predictor subset. As trees are built, progressively smaller predictor subsamples are drawn and used to predict earlier data splits forming “parent” and “child” nodes. The number of predictors at each node will be determined by the square root of the total number of predictors to limit over-fitting [96] and an error minimization criterion will be applied to select the predictor and cut point at each node of the decision tree that optimizes binary splits. This iterative process will continue down the tree until node size is equal to 10% of the total study sample. A 10-fold cross-validation will also be run as a preliminary validation of estimates.

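### The EHR predictors in E3.3 include a chart Suicidality item that largely restates case-control status, which inflates the EHR-only model and biases the test of added value against the cognitive data

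*Combined protocol and SAP*

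**What the plan says.** **The task.** E3.3 (General approach) states: "The goal is to predict participants with: 1) history of attempt, 2) suicidal ideation without history of attempt, 3) no history of STBs". The added-value test is also in E3.3: "Models will be constructed both with, and without, Aim 1 & 2 measures to test if their inclusion improves suicide prediction". The model with the highest AUC is taken as best.

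**The inputs.** E3.3 lists "Aggregated EHR data (Section D6.2) and subject-level performance outcomes on the reward expectancy scanned task", followed by the other tasks. The document has no section D6.2; EHR variables are constructed in D5.2, which says "EHR measures are listed in Table 5". The last block of Table 5 is headed "Mental Health (Current and Lifetime", and its last entry is Suicidality. Inpatient mental-health use is in the utilization block. D5.1 presents the extraction as one of predictors, and no section withholds any Table 5 variable from the classifiers.

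**The window.** Under D5, at each extraction "data for the current month, and for each of the 12 prior months will be extracted". D5.2 averages monthly sums by quarter and year. A categorical variable that changes within a period takes the value that prevails over it.

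**The selection.** Under D2.1, STB participants enter within two weeks of an episode that is "indicated on hospital chart and confirmed by administration of the Columbia Suicidal Severity Rating Scale". Controls enter on "No evidence of current suicidality in the medical record" and no current endorsement on the C-SSRS. D3.1.2 finds controls through CPRS, and D5.1 takes the EHR predictors from CPRS.

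**The concern.** The chart entry for current suicidality helps to make someone a case, and its absence helps to make someone a control. Table 5 then collects that entry as an input to a model of case status. The lifetime entry has a similar problem, because absence of any STB history is how E3.3 words its third class.

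Two results are at stake. The first is the comparison with and without cognitive measures. If the EHR-only model already scores high because of how participants were selected, the cognitive data have less room to show a gain. The second is the reported EHR performance, along with the risk factors that E3.3 hopes to read from feature contributions. A leading feature could be the label itself. Ten-fold cross-validation and the bootstrap would not reveal this, because the leak is present in every fold.

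**Working it through.** **No figure to reproduce.** E3.3 gives no sample size, power or expected AUC for either model. It cites EHR models in general as exceeding an AUC of 0.70.

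**Inputs.**
- Class sizes: 30 attempt, 30 ideation, 60 controls. These are the upper limits given under E3.1 and E3.2; E3.3 gives none.
- s = share of STB participants carrying the flag; f = share of controls carrying it. The documents give neither, so both are assumptions.
- The flag is taken to be equally common in the attempt and ideation classes, because the documents do not say that the item records attempts.

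**Formula.** For a binary flag, counting ties as one half:

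AUC = s(1 - f) + 0.5[sf + (1 - s)(1 - f)] = (1 + s - f)/2

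**Perfect flag (s = 1, f = 0).**
- STB v control: (1 + 1 - 0)/2 = 1.00
- Attempt v ideation: (1 + 1 - 1)/2 = 0.50
- Attempt v rest: (30 × 0.50 + 60 × 1.00)/90 = 0.833; ideation v rest is the same
- Macro one-versus-rest: (0.833 + 0.833 + 1.00)/3 = 0.889
- Mean pairwise: (0.50 + 1.00 + 1.00)/3 = 0.833

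The room left above the flag is 1 - 0.889 = 0.11 on the macro measure and 1 - 0.833 = 0.17 on the pairwise measure. All of it lies in attempt versus ideation. E3.3 does not say which multiclass AUC it would use.

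**Imperfect flags (assumed).**

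| s | f | STB v control | Attempt v ideation | Attempt v rest | Macro |
|---|---|---|---|---|---|
| 100% | 0% | 1.00 | 0.50 | 0.833 | 0.889 |
| 100% | 20% | 0.90 | 0.50 | 0.767 | 0.811 |
| 90% | 0% | 0.95 | 0.50 | 0.800 | 0.850 |
| 90% | 20% | 0.85 | 0.50 | 0.733 | 0.772 |
| 80% | 30% | 0.75 | 0.50 | 0.667 | 0.694 |

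Even the last row puts one variable at 0.75 for STB versus control.

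**Inpatient mental-health use.** With an assumed 50-100% of STB participants and 0-20% of controls admitted, the AUC runs from (1 + 0.5 - 0.2)/2 = 0.65 to (1 + 1 - 0)/2 = 1.00. It reaches 1.00 only if every STB participant and no control was admitted.

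**After the fix.** The AUC cannot be computed, because the documents give no expected EHR-only performance in this sample.

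**The case against.** The strongest reply has five parts.

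1. **The task has three classes.** A reader might infer that the EHR-only model succeeds by construction and that the added-value test is void. The documents do not support that. Nothing says the item separates attempt from ideation, and that contrast is the one E3.2 targets. This stands.
2. **The flag need not be perfect.** The D5.2 aggregation rule can override a current entry that first appears in the enrolment month. Controls are screened for current suicidality only, so some may carry a lifetime entry. This stands, and is why a range is shown. It does not remove the leak. A control with past STBs also does not fit the third class as E3.3 words it, which is a separate mismatch between D2.1 and E3.3.
3. **Inpatient use is not a class definition.** A reader might infer that it is, because the participant-group paragraph under E3.1 describes the STB group as hospitalized. But D2.1 also admits people identified as outpatients, and no criterion bars controls from inpatient care. It is a strong proxy only, and the two sections must be reconciled.
4. **A5 concerns longitudinal outcomes.** For later outcomes, baseline suicidality and recent utilization come first in time and are legitimate predictors. This stands: the leak affects the cross-sectional classification in E3.3, not every model under A5.
5. **The aim is exploratory.** E3.3 is labelled so and defers replication to an independent sample. Table 5 also serves follow-up extractions, so Suicidality may be meant partly as an outcome. This lowers the stakes, but the plan never says the item is left out of the predictors.

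**Conclusion.** The concern holds in a limited form. Followed as written, E3.3 includes among its inputs a chart item that largely restates case versus control status. From that item alone, the STB-versus-control AUC is 1.00 with a perfect flag and 0.75 to 1.00 over the assumed range. The EHR-only model is inflated, and the comparison with and without cognitive measures is biased towards no added value.

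The comparison is compromised, not void. If the item does not split attempt from ideation, the flag leaves that pair at 0.50, and its macro one-versus-rest AUC is at most about 0.89. If the item is coded with attempt detail, the leak would reach that pair too; the documents do not say.

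The figures rest on the assumed flag frequencies. The macro values also rest on class sizes of 30, 30 and 60, which could shift because E3 pools Aim 2 data with another protocol. No treatment conclusion depends on this analysis, but the correction is worth making before any model is fitted.

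**What to change.** Change E3.3 only, for the cross-sectional classification:

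- Exclude the Suicidality item, current and lifetime, from the predictors.
- Use only EHR months that end before the index episode, with the matched calendar month as the cut-off for controls. This also removes index-episode admissions and other utilization.
- Report attempt versus ideation separately from STB versus control.
- Say that these variables stay available for any A5 model of later, longitudinal outcomes.

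Also reconcile D2.1 with the participant-group paragraph under E3.1 on whether outpatients belong to the STB group, and correct the reference to D6.2.

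**Cost.** Analysis-plan wording only. Extraction is already monthly, so no new data are needed and D5 can stay as it is. Reported AUCs will be lower, and this one exploratory analysis loses the index-month EHR data.

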- Brain and behavioral correlates of decision-making, impulsivity, and executive control at baseline will differ between Veterans with suicidality and non-suicidal Veteran controls.

- Improvement in suicide symptoms after treatment will be predicted by brain and behavioral correlates of decision-making and executive control at baseline.
- Improvements in suicidality will be associated with functional changes in decision-making circuits.
- Machine learning models predicting longitudinal outcomes that merge brain, cognitive, and electronic health record (EHR) data will outperform models based solely on EHR.

B. BACKGROUND

The tragedy of Veteran suicide cannot be overstated. Twenty Veterans die each day of suicide [1]. Suicide in female Veterans has increased substantially in the last 5 years [1]. Suicide attempt rates are also climbing. The Veterans' Health Suicide Prevention Application Network (SPAN) reported that over 900 suicide attempts per month occurred in 2014 - an unacceptable increase from 600 per month in prior reports [1]. The presence of a single episode of suicidal ideation or attempt places an individual at greatly increased future risk [2]. Research in civilian populations demonstrated that suicide attempters are 38 times more likely to die of suicide than those without history of attempts [3]. In the year following a suicide attempt, 0.8 – 2.6% of previous attempters died of suicide; mortality estimates 9 years post attempt are as high as 5-11%[4].

One estimate suggests that approximately 15% of all individuals with one or more suicide attempts will eventually die of suicide [5].

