Support Vector Machines (SVM) A supervised non-linear kernel function is used to transform the input data to a high-dimensional space, wherein individual observations are plotted as points in this n-dimensional space (n=size of predictor set). Classification is performed by identifying the mapping function that maximally segregates data classes. The choice of an underlying kernel function and its parameters can be used to balance the trade-off between classifier performance and complexity of dimensional space. Probability estimates, tuning of kernel, and regularization parameters will be computed by means of cross-validation.

Model comparisons Receiver Operating Characteristics (ROC) will be used to compare accuracy of models’ predictions. The area under the ROC curve statistic (AUC) will be used as the metric of algorithm classification performance, the model with the highest AUC value will be considered the best-fitting model. Models will undergo 10-fold cross-validation and bootstrap optimization analyses to measure model robustness.

Model interpretation: Although building models to predict STBs is the primary focus of this Aim, these models can yield additional valuable information that will advance our understanding of suicidal phenotypes. As post-hoc analyses, we will analyze the approach and strategy used by each of the classifiers listed above to predict STB. Different machine learning algorithms have various degrees of predictability. In Logistic Regression for example, studying the regression coefficients can provide insights about the information content of the features selected by the model for classification. Specific algorithms have been developed for other classifiers that estimate feature contribution [97]. This would lead to a

data-driven and unbiased identification of risk factors, many of which could be modifiable by simple interventions and as a result could reduce the risk of STBs.

Design considerations and alternative approaches: This study sample size is small because of budgetary restrictions. We recognize that this decreases the likelihood that models will generalize to an independent sample. A transdiagnostic participant sample is planned because

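### E3.3 compares models with and without cognitive measures only by which AUC is highest; in simulation, pure-noise measures win in roughly 18–43% of runs

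*Combined protocol and SAP*

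**What the plan says.** The A5 exploratory hypotheses include this one: "Machine learning models predicting longitudinal outcomes that merge brain, cognitive, and electronic health record (EHR) data will outperform models based solely on EHR".

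The corresponding analysis is E3.3, which is headed exploratory. Its rationale paragraph states the comparison: "Models will be constructed both with, and without, Aim 1 & 2 measures to test if their inclusion improves suicide prediction". The algorithms are elastic-net logistic regression, random forest and a support vector machine, so there are six models once each is fitted with and without the added measures. The outcome has three classes: history of attempt, ideation without attempt, and no history of suicidal thoughts or behaviors.

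The model-comparisons paragraph makes AUC the performance metric and says that "the model with the highest AUC value will be considered the best-fitting model". It continues: "Models will undergo 10-fold cross-validation and bootstrap optimization analyses to measure model robustness".

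On tuning, the support vector machine paragraph says: "Probability estimates, tuning of kernel, and regularization parameters will be computed by means of cross-validation". The general-approach paragraph places training, cross-validation and optimization on the same discovery data set. Replication in an independent sample is left to future studies.

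**The concern.** The plan announces a test of whether the added measures improve prediction, but supplies only a ranking. Two cross-validated AUCs from about 120 people are both noisy, and one will almost always exceed the other. If the larger one settles the question, useless measures will be credited with an improvement some of the time, and nothing in the plan limits how often.

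Two further gaps affect the number to be reported. If settings or algorithms are chosen on the same folds that give the AUC, the winning AUC is biased upward, and the plan does not say whether tuning is nested. With three outcome classes an AUC can be formed in several ways, and the plan does not choose one.

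At stake is what the report says about the value of the cognitive battery for prediction, and which markers are carried into later studies.

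**Working it through.** The plan gives no error rate, power or sample size for E3.3, so there is no figure to reproduce. The behavior of the highest-AUC rule was simulated.

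**Inputs**
- Participants: 120 (30 ideation, 30 attempt, 60 controls), from E1. E3.3 states no number, and E3 says Aim 2 data will be combined with another protocol, so 120 is an assumption.
- EHR predictors: Table 5 has 29 rows (5 + 5 + 5 + 14), before quarterly and yearly averaging. Assumed 29, range 10 to 100.
- Cognitive predictors: E3.3 lists six tasks without fixing the scores. Assumed 8, range 8 to 20, all pure noise.
- EHR-only AUC: E3.3 cites values above 0.70 for existing EHR models and gives none for this sample. Assumed about 0.70, range from no signal to about 0.87.
- Resampling: stratified 10-fold, as the plan says. The same folds were used for both predictor sets except in one scenario.
- Settings: elastic net (18 settings), radial SVM (9 settings), and random forest with the square root of the predictor count per split and leaves of at least 10% of the sample, following E3.3. The best AUC over each grid was taken on the same folds.
- Outcome: two-class contrasts, because the plan does not define a three-class AUC.

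**Quantity.** False-credit rate = runs in which the highest-AUC model of the six contains the noise predictors ÷ all runs. There were 260 runs per scenario, and 176 with 100 EHR predictors. Monte Carlo 95% error = 1.96 × √(p(1 − p)/R). For the base case this is 1.96 × √(0.273 × 0.727/260) = 0.054, or about 5 points.

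| Scenario | Mean best AUC, EHR only | Mean best AUC, EHR + noise | Noise model wins |
|---|---|---|---|
| Base: 60 v 60, 29 + 8 predictors | 0.707 | 0.697 | 27.3% |
| One strong EHR predictor | 0.761 | 0.759 | 18.5% |
| Stronger EHR signal | 0.865 | 0.858 | 23.5% |
| 20 noise predictors | 0.712 | 0.695 | 25.0% |
| 10 EHR predictors | 0.710 | 0.697 | 27.7% |
| 100 EHR predictors | 0.719 | 0.714 | 29.5% |
| Attempt v rest (30 v 90) | 0.705 | 0.699 | 30.4% |
| Attempt v ideation (30 v 30, 60 people) | 0.707 | 0.703 | 34.2% |
| EHR with no signal | 0.570 | 0.573 | 40.8% |
| Base, different folds for the two sets | 0.707 | 0.702 | 42.7% |

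The rate stays below one half mainly because noise predictors usually cost a little accuracy (0.707 to 0.697 in the base case). It rises when there is no EHR signal to dilute, or when separate folds add noise to the difference.

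**Other readings**
- If improvement means that any one of the three algorithms gains, the rate is 51.2% in the base case and 46% to 69% across scenarios.
- With fixed settings instead of same-fold tuning, the base case gives 31.2% against 27.3%. Same-fold tuning therefore does not drive the rate.
- Same-fold tuning and picking the best of several models do affect the absolute AUC. With no signal at all, the mean best AUC was 0.570 to 0.573 instead of 0.50. A separate simulation with smaller tuning grids gave 0.535 to 0.539.

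**Effect of a test.** A paired DeLong test on the two best models' cross-validated scores was then required (two-sided p < 0.05, in favor of the combined model). This cut false declarations to 0.8% in the base case and 0% to 2.3% across scenarios. Nested cross-validation was not simulated.

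**The case against.** The strongest reply is that this is openly exploratory work: "Three types of supervised machine learning models (described below) will be used for this exploratory analysis". The plan calls the sample a discovery set, admits that it is small and may not generalize, defers replication, plans a bootstrap, and raises precision-recall measures as an alternative to AUC. All of this stands, and it keeps the severity low. None of it changes how the with/without comparison is decided. The bootstrap is for robustness and is not described as an interval for the difference.

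A second reply is that the highest-AUC sentence only names a best-fitting model and does not say that cognitive data are useful. That is a fair reading of the sentence alone. But E3.3 gives no other criterion for the comparison it announces.

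Some stronger readings are tempting, and the documents do not support them:
- A reader might infer a false-credit rate of about 40%, or close to a coin toss. Under the stated highest-AUC rule, rates near 40% appeared only with no EHR signal or unshared folds. A separate simulation gave 40% to 42%, but its signal strength and fold sharing were not recorded.
- A reader might infer that tuning and evaluation share folds. The plan does not say so; it is silent on nesting.
- A reader might call a three-class AUC undefined. It is only unspecified, since standard averages exist.
- A reader might infer that the A5 conclusion would be nearly worthless. The link to A5 is loose: A5 concerns longitudinal outcomes and includes brain data, whereas E3.3 classifies history groups and lists EHR and task-performance data.

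**Conclusion.** The point holds as a modest one. E3.3 sets out to test an improvement and offers only the highest AUC to judge it. Applied to pure-noise cognitive predictors, that rule favors the noise-containing model in roughly 18% to 43% of runs, and in about 27% with EHR-only AUC near 0.70 and shared folds.

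These figures rest on an assumed 120 participants (60 in one contrast), two-class outcomes, and assumed predictor counts, EHR signal and fold sharing. Each rate carries a Monte Carlo error of about 5 to 7 points. Even the low end is high for something reported as a test.

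The winning AUC may also be optimistic, because nesting is not specified, and the three-class metric needs a definition. None of this touches the treatment comparison in Aim 1.

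**What to change.** Amend the model-comparisons paragraph of E3.3:
1. Keep AUC, defined as the macro-averaged one-v-rest AUC over the three classes.
2. Use nested 10-fold cross-validation, with tuning and algorithm choice in the inner loop.
3. Use the same outer folds with and without the added measures. Report the AUC difference as a paired estimate with a 95% interval (bootstrap or DeLong-type).
4. Claim improvement only if the interval excludes zero, and keep the exploratory label.

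The cost is a paragraph of text and more computing time, with no new data or visits. Reported AUCs will be slightly lower.

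The real price is a lower chance of declaring a small true gain. The separate simulation put the standard deviation of the AUC difference at 0.026 to 0.028. As a rough guide, the observed gain would need to exceed about 1.96 × 0.026 = 0.051 to 1.96 × 0.028 = 0.055. That limit comes from the sample size, and the interval would show it openly.
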